7.1.2 Treatment Period

The total duration of treatment will be 6 months. Eligible patients will be randomized 1:1 prior to Baseline to receive SEL-212 or KRYSTEXXA.

Study patients in the SEL-212 arm will receive study drug every 28 days coinciding with Day 0 of each Treatment Period for a total of up to 6 infusions of SEL-212.

Study patients in the KRYSTEXXA arm will receive study drug according to the manufacturer's prescribing information, i.e., every 14 days coinciding with Day 0 and Day 14 of each Treatment Period for a total of up to 12 infusions of KRYSTEXXA.

Prior to infusion, all patients will receive a standardized regimen of premedication to minimize the potential for infusion reactions during study drug administration. After completing the study drug infusions, patients will remain at the investigational site for at least 1 hour for safety assessments.

Refer to [Section 10](#) for details about study drug administration.

With each dose, a blood sample will be drawn for assessment of SUA level immediately prior to infusion (ie, Time 0h) with SEL-212 or KRYSTEXXA, 1 hour after the infusion of the second component of SEL-212 or of KRYSTEXXA is completed. SUA levels will be assessed through additional post-infusion blood samples at pre-determined time points. Every effort will be made to obtain blood samples at the same time of day of each study visit.

[figure not shown]
Gout flares will be assessed at every visit. QoL and joint swelling and tenderness will be assessed on Day 0 of Treatment Period 1 and 4, and at the end of Treatment Period 6. Assessments of qualitative endpoints (health questionnaires and joint assessment) will be conducted on an assessor-blinded basis.

On dosing days, safety laboratory samples will be collected pre-infusion and per Schedule of Events in both the SEL-212 arm and the KRYSTEXXA arm. Concomitant medications and procedures and adverse events (AEs) will be monitored continuously during the study.

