10.6 Administration

10.6.1 SEL-212

Before administration of SEL-212, patients will be premedicated with antihistamines and steroids as described in [Section 10.5](#).

Patients will receive treatment with SEL-212 on Day 0 of each Treatment Period for a total of 6 doses of study drug.

All study drugs should be administered through the same IV access. All blood samples should be drawn from an alternative venous access.

If an infusion reaction occurs, Investigators are permitted to use concomitant medications or treatments deemed necessary to provide adequate patient care. Investigators should also utilize the infusion reaction lab kit provided in the Study Operations Manual to collect additional blood specimens. In the case of a Grade 3 or 4 infusion reactions occurring during an infusion, the administration of study drug should be immediately discontinued, and the affected patient should be treated according to the clinical trial site's protocol for infusion reactions (e.g., monitoring, administration of antihistamines, corticosteroids, fluids and epinephrine, as clinically indicated).

The reconstituted SEL-110.36 will be withdrawn from the vial and dosed via IV infusion with a syringe infusion pump utilizing an appropriately sized syringe. SEL-110.36 will be infused at a rate of 3.0 mL/hr for the first 30 minutes, then a rate adequate to deliver the remaining dose volume over a period of 60 minutes concurrently with 125 mL normal saline. Following the infusion of SEL-110.36, the main IV line must be flushed with normal saline prior to the start of the SEL-037 infusion. Refer to the Study Operations Manual for instructions regarding infusions for patients with medical history involving cardiovascular comorbidities.

SEL-037 infusion will start within 15 minutes after completion of the SEL-110.36 infusion. SEL-037 will be infused via infusion pump over a time period of no less than 120 minutes. If an infusion reaction occurs during the administration of SEL-037, the infusion may be slowed, or stopped and restarted at a slower rate at the discretion of the physician. Following the infusion of SEL-037, the main IV line must be flushed with normal saline.

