12.2.4 Follow-up of Adverse Events

The Investigator is required to proactively follow each patient and provide further information in regards to AEs and SAEs. All AEs and SAEs will be followed until 30 days after the last dose of study drug, resolution of the event, until the condition stabilizes, until the event is otherwise explained, or until the patient is lost to follow-up, whichever occurs earlier. Once resolved, the appropriate CRF entries and event reporting forms will be updated, as appropriate.

All AEs and SAEs documented at a previous visit/contact and designated as ongoing will be reviewed at subsequent visits/contacts. The Investigator will ensure that follow-up includes any supplemental investigations as may be indicated to elucidate the nature and/or causality of the AE or SAE. This may include additional laboratory tests or investigations, histopathological examinations, or consultation with other health care professionals.

STUDY: SEL-212/202
VERSION: 3.0

EFFECTIVE DATE

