13.5.3 Laboratory Assessments

Laboratory data will be summarized by the type of laboratory test and will be presented for each scheduled visit stratified by treatment group (SEL-212 or KRYSTEXXA). Normal reference

ranges and markedly abnormal results will be used in the summary of laboratory data. Data will be flagged according to the reference limits (High or Low), if applicable. Changes from baseline will be presented for each post-baseline visit. Shift tables of the number of patients with low/normal/high values at each scheduled post-baseline visit compared to the low/normal/high categorization at baseline will be provided by treatment group (SEL-212 or KRYSTEXXA).

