5.7. General Methods

SAS® version 9.4 or higher will be used for all statistical analyses and tabulations.

In general, summaries will present data by treatment group and assessment time where appropriate.

Unless stated otherwise, descriptive summaries will include n, mean, standard deviation, median, minimum and maximum for continuous variables, and n and percent for categorical variables. If there are multiple assessments collected on the same scheduled time within the visit windows defined for each assessment, the average of these assessments will be used. For tabulated safety summaries, only the scheduled assessments will be included in the summary tables.

Data collected at unscheduled visits will be included in the data listings but will not be included in the analyses or by treatment summaries.

Adverse events and medical history will be coded according to the most recent version of Medical Dictionary for Regulatory Activities (MedDRA). Prior and concomitant medications will be coded using the most recent WHO Drug Dictionary version. The actual version of MedDRA and WHO drug used will be noted on the corresponding actual output.

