8.4. Laboratory Evaluations

Laboratory data will be summarized by the type of laboratory test and will be presented for each scheduled visit by treatment group (SEL-212 or KRYSTEXXA®). Normal reference ranges and markedly abnormal

This document is confidential.

results will be used in the summary of laboratory data. Data will be flagged according to the reference limits (High or Low), if applicable. Changes from baseline will be presented for each post-baseline visit. Shift tables of the number of patients with low/normal/high values at each scheduled post-baseline visit compared to the low/normal/high categorization at baseline will be provided by treatment group (SEL-212 or KRYSTEXXA®).

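### The only fully specified patient count in SAP 8.4 is a low/normal/high shift by scheduled visit, so further rises in patients already High and unscheduled peaks reach no laboratory count

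*SAP*

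**What the plan says.** SAP 8.4 lists five things for laboratory data: by-visit summaries; use of normal ranges and markedly abnormal results; High/Low flags against reference limits; change from baseline at each post-baseline visit; and "Shift tables of the number of patients with low/normal/high values at each scheduled post-baseline visit compared to the low/normal/high categorization at baseline". Protocol 13.5.3 has the same content, stating that normal reference "ranges and markedly abnormal results will be used in the summary of laboratory data". Neither document gives a limit or a table layout for markedly abnormal.

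SAP 5.7 sets the rules for which values enter the tables. Where several assessments fall on the same scheduled time, "the average of these assessments will be used". Next, "For tabulated safety summaries, only the scheduled assessments will be included in the summary tables". Finally, "Data collected at unscheduled visits will be included in the data listings but will not be included in the analyses or by treatment summaries".

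The protocol nevertheless foresees tests outside the schedule. On adverse event follow-up, Protocol 12.2.4 says: "This may include additional laboratory tests or investigations, histopathological examinations, or consultation with other health care professionals". For an infusion reaction, Protocol 10.6.1 tells investigators to "utilize the infusion reaction lab kit provided in the Study Operations Manual to collect additional blood specimens"; the analytes are not given.

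Protocol 12.2.2.6 has clinically significant laboratory findings reported as adverse events, on the investigator's judgement. Protocol 12.2.2.3 grades adverse events by the Rheumatology Common Toxicity Criteria (RCTC) v2.0, and SAP 8.3 tabulates TEAEs by maximum intensity. Protocol 12.2.1.5 names hyperlipidemia, worsening renal function tests, proteinuria and leukopenia as events of special interest (AESIs) if the investigator finds them clinically significant.

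**The concern.** A three-category shift records only that a value crossed a reference limit. It cannot record further worsening in someone already outside the limit, and it does not separate a trivial crossing from a large one. Because it is taken visit by visit, it never gives the number of patients who worsened at any time. With unscheduled results confined to listings, tests prompted by a clinical problem contribute to no laboratory table.

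Laboratory testing is a named safety assessment (Protocol 6.2.3), and four laboratory findings are AESIs. A reader of the planned laboratory tables could not tell how many patients per arm were abnormal at entry and got worse, or how many reached a given severity at any point. SAP 8.6 handles ECG data differently: it counts patients beyond stated QTc limits, for both value and change.

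**Working it through.** No figure in the plan bears on this point, so there is none to reproduce. The check is what each planned output does with a given laboratory course.

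| Course after baseline | Shift table | By-visit change summary | TEAE/AESI tables |
|---|---|---|---|
| Normal to 1.1x ULN, scheduled | one shift | within group statistics | if judged clinically significant |
| Normal to 8x ULN, scheduled | the same one shift | within group statistics; may be the maximum | if judged clinically significant |
| High at entry, rises further, scheduled | no shift | within group statistics; may be the maximum | if judged clinically significant |
| Peak at an unscheduled test only | excluded | excluded | if judged clinically significant |

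The by-visit maximum (SAP 5.7) shows the largest value in the arm at that visit, not how many patients had a large one.

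**1. Patients already High.** Exclusion 14 (Protocol 8.2) removes ALT or AST above 3x ULN, so values above 1x and up to 3x ULN are allowed at entry. In the SEL-212 grid (Appendix A) the post-baseline safety-laboratory visits are Day 21 of Treatment Periods 1 to 6 (6) plus Day 28 of Treatment Period 6 (1): 6 + 1 = 7, not counting Early Termination. Protocol 7.1.2 also says that on dosing days "safety laboratory samples will be collected pre-infusion and per Schedule of Events". If that adds Day 0 of Periods 2 to 6 (5), the total is 7 + 5 = 12. On either reading, a patient High at baseline whose enzymes rise further contributes 0 shifts.

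**2. Any-time count against by-visit counts.** Illustration only; the rates are assumed. Take 75 patients, all Normal at baseline, 7 visits, and a chance q of a transient abnormality at each visit, independent between visits. Expected patients in each by-visit table = 75q. Expected patients abnormal at any visit = 75 × [1 − (1 − q)^7].

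| q | Each by-visit table | Any visit |
|---|---|---|
| 1% | 0.75 | 5.1 (6.8%) |
| 2% | 1.5 | 9.9 (13.2%) |
| 5% | 3.75 | 22.6 (30.2%) |

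At the other extreme, if every abnormality is sustained, the last by-visit table equals the any-visit count and nothing is lost.

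**3. Averaging.** Illustration only: values of 8x and 2x ULN for one scheduled time average to (8 + 2)/2 = 5x. The category stays High, but the tabulated maximum falls.

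**The case against.** The strongest reply is that the shift table does not stand alone. Markedly abnormal results are to be used in the summary and could count large rises within High. Changes from baseline are shown at every post-baseline visit with mean, SD, median, minimum and maximum. Above all, clinically significant worsening is reported as an adverse event whatever the category or visit, graded, and tabulated by maximum intensity, with four laboratory findings tracked as AESIs. What stays uncounted is mainly change that the investigator thought unimportant.

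Much of this stands. A reader might infer that SAP 8.4 captures laboratory worsening through shift tables and nothing else; the documents do not support that. But without limits the markedly abnormal count cannot be programmed reproducibly, group statistics do not count patients, and the adverse event route rests on judgement by investigators who know the assignment (Protocol 7.6.1). SAP 8.3 also leaves the AESI definition to the medical monitor before database lock. None of these outputs gives an any-time count per patient from the laboratory values themselves.

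Two objections to the remedy are also fair. Unscheduled testing may differ between open-label arms, so a count that includes it has its own ascertainment problem; hence the scheduled-only count beside it. And neither document states numerical RCTC laboratory limits (Protocol 12.2.2.3 refers to the operations manual for detail), so the cut-offs are the sponsor's to choose.

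**Conclusion.** The point holds as a gap in descriptive safety reporting that is cheap to close. No planned laboratory table counts further worsening in a patient already abnormal, counts patients by severity, or counts them at any time on study, and unscheduled peaks enter none of them.

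Its size cannot be fixed from the documents. They give no share of patients abnormal at entry, no rate of unscheduled testing and no rate of repeats. The certain part is structural: 0 shifts for a High patient who rises. The any-visit figures above depend on assumed, independent rates, and the loss they show vanishes if abnormalities persist.

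Two further inferences should be resisted. A reader might take the stretch of each SEL-212 period without a scheduled safety laboratory test as a measure of the loss. That describes the protocol's sampling, which SAP 8.4 does not set and the fix would not change. A reader might also infer that the comparison between arms is biased. Nothing in the documents shows that. Nor is a visit count offered for the Krystexxa arm: as it reads in text, that grid has an extra mark under the End of Study column, which is a telephone contact, so its marks cannot be counted reliably. The primary analysis is not affected.

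**What to change.** In SAP 8.4 add one descriptive table by arm: worst post-baseline grade by baseline grade for ALT, AST, creatinine, lipids (triglycerides, LDL, total cholesterol), WBC and urinary protein. Give the number and percentage of patients whose grade worsens by at least 1 and by at least 2.

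- **Limits.** Write them into SAP 8.4: RCTC v2.0 grades or, where those have no laboratory limit, multiples of ULN or baseline stated in advance by the sponsor. Possible choices, found in neither document, are ALT/AST >3x, >5x and >8x ULN and creatinine ≥1.5x, ≥2x and ≥3x baseline. Use the same limits to define markedly abnormal.
- **Values used.** Exempt this table from the averaging and scheduled-only rules of SAP 5.7, so that it takes every post-baseline result. Show the scheduled-only count beside it.
- **Local laboratories.** SAP 7.4.1 mentions local testing without saying which tests; use the local range for any local result.

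Keep all existing tables. The cost is SAP wording and modest programming: grading the analytes, bringing in unscheduled results and attaching local ranges where needed. No extra sampling is required. The remaining drawback is possible unequal ascertainment between arms, which the paired counts make visible but do not remove.

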8.5. Vital Signs

Summary tables of the actual values and changes from baseline will be provided for each vital sign parameter at each scheduled visit by treatment group (SEL-212 or KRYSTEXXA®).

8.6. ECG

For each 12-lead ECG variable the actual value and the change from baseline will be summarized for the scheduled visits by treatment group (SEL-212 or KRYSTEXXA®).

Frequency tables of abnormal clinically significant evaluations as well as the number and percentage of patients with noteworthy QTcF/QTcB values (> 450 , > 480 and > 500 ms) and of patients with noteworthy QTcF/QTcB changes from baseline (≥ 30 but < 60 ; ≥ 60 ms) will be provided.

8.7. Tophus Assessment

For each tophus assessment variable (including total number, location, palpation and appearance) the actual value and the change from baseline will be summarized for the scheduled visits by treatment group (SEL-212 or KRYSTEXXA).

8.8. Physical Examination

A full physical examination will be performed at Screening, end of treatment period 6 or early termination visit and directed physical examinations will be collected at the beginning of each treatment period cycle.

Physical examination results will be presented in data listings.

This document is confidential.

9. DSMC and Interim Analyses

An independent Data and Safety Monitoring Committee (DSMC) will be formed by charter in a separate document to assist in reviewing safety data and provide recommendations to the Sponsor regarding study drug dose adjustment or study termination as needed.

As discussed in section 2.2, An interim analysis will be conducted when 100% of patients are scheduled to have completed 3 months of study treatment (ie scheduled to have completed Treatment Period 4 Day 0 visit).

This document is confidential.

10. Reference List

Ware JE Jr, Sherbourne CD. The MOS 36-item short-form health survey (SF-36). I. Conceptual framework and item selection. *Med Care*. 1992 Jun;30(6):473-83.

This document is confidential.

11. Programming Considerations

All tables, data listings, figures (TFLs), and statistical analyses will be generated using SAS® for Windows, Release 9.4 (SAS® Institute Inc., Cary, NC, USA). Computer-generated table, listing and figure output will adhere to the following specifications.

11.1. General Considerations

- Each output will be stored in a separate file.
- Output files will be delivered in Rich Text Format.
- Numbering of TFLs will follow ICH E3 guidance

11.2. Table, Listing, and Figure Format

11.2.1. General

- All TLFs will be produced in landscape format, unless otherwise specified.
- All TLFs will be produced using the Courier New font, size 8
- The data displays for all TLFs will have a minimum 1-inch margin on all 4 sides.
- Headers and footers for figures will be in Courier New font, size 8.
- Legends will be used for all figures with more than 1 variable, group, or item displayed.
- TLFs will be in black and white (no color), unless otherwise specified
- Specialized text styles, such as bolding, italics, borders, shading, and superscripted and subscripted text, will not be used in the TLFs, unless otherwise specified. On some occasions, superscripts 1, 2, or 3 may be used (see below).
- Only standard keyboard characters will be used in the TLFs. Special characters, such as non-printable control characters, printer-specific, or font-specific characters, will not be used. Hexadecimal-derived characters will be used, where possible, if they are appropriate to help display math symbols (e.g., μ). Certain subscripts and superscripts (e.g., cm^2 , C_{max}) will be employed on a case-by-case basis.
- Mixed case will be used for all titles, footnotes, column headers, and programmer-supplied formats, as appropriate.

11.2.2. Headers

- All output should have the following header at the top left of each page:

SELECTA Biosciences
Protocol SEL – 212/202
Draft/Final Run <date>

- All output should have Page n of N at the top or bottom right corner of each page. TFLs are internally paginated in relation to the total length (i.e., the page number should appear sequentially as page n of N, where N is the total number of pages in the table).
- The date output was generated should appear along with the program name as a footer on each page.

This document is confidential.

11.2.3. Display Titles

- Each TFL is identified by the designation and a numeral. (i.e., Table 14.1.1). ICH E3 numbering is strongly recommended, but sponsor preferences are obtained before final determination. A decimal system (x.y and x.y.z) are used to identify TFLs with related contents. The title is centered. The analysis set are identified on the line immediately following the title. The title and table designation are single spaced. A solid line spanning the margins will separate the display titles from the
- Column headers. There will be 1 blank line between the last title and the solid line.

Table x.y.z
First Line of Title
Second Line of Title if Needed
(ITT Analysis Set)

11.2.4. Column Headers

- Column headings are displayed immediately below the solid line described above in initial upper-case characters
- In the case of efficacy tables, the variable (or characteristic) column will be on the far left followed by the treatment group columns and total column (if applicable). P-values may be presented under the total column or in separate p-value column (if applicable). Within-treatment comparisons may have p-values presented in a row beneath the summary statistics for that treatment.
- For numeric variables, include “unit” in column or row heading when appropriate.
- Analysis set sizes will be presented for each treatment group in the column heading as (N=xx) (or in the row headings, if applicable). This is distinct from the ‘n’ used for the descriptive statistics representing the number of patients in the analysis set.
- The order of treatments in the tables and listings will be Placebo first in the case of placebo controlled studies and Active comparators first in the case of active comparator trials, followed by a total column (if applicable).

11.2.5. Body of the Data Display

11.2.5.1. General Conventions

Data in columns of a table or listing are formatted as follows:

- Alphanumeric values are left-justified;
- Whole numbers (e.g., counts) are right-justified; and
- Numbers containing fractional portions are decimal aligned.

11.2.5.2. Table Conventions

- Units will be included where available

This document is confidential.

- If the categories of a parameter are ordered, then all categories between the maximum and minimum category are presented in the table, even if n=0 for all treatment groups in a given category that is between the minimum and maximum level for that parameter. For example, the frequency distribution for symptom severity would appear as:

Severity Rating	N
severe	0
moderate	8
mild	3

Where percentages are presented in these tables, zero percentages will not be presented and so counts of 0 will be presented as 0 and not as 0 (0%).

- If the categories are not ordered (e.g., Medical History, Reasons for Discontinuation from the Study, etc.), then only those categories for which there is at least 1 patient represented in 1 or more groups are included.
- An Unknown or Missing category are added to each parameter for which information is not available for 1 or more patients.
- Unless otherwise specified, the estimated mean and median for a set of values are printed out to 1 more significant digit than the original values, and standard deviations are printed out to 2 more significant digits than the original values. The minimum and maximum should report the same significant digits as the original values. For example, for systolic blood pressure:

N	XX
Mean	XXX.X
Std Dev	X.XX
Median	XXX.X
Minimum	XXX
Maximum	XXX

- P-values are output in the format: "0.xxx", where xxx is the value rounded to 3 decimal places. Every p-value less than 0.001 will be presented as <0.001. If the p-value are less than 0.0001, then present as <0.0001. If the p-value is returned as >0.999, then present as >0.999
- Percentage values are printed to one decimal place, in parentheses with no spaces, one space after the count (e.g., 7 (12.8%), 13 (5.4%)). Pre-determine how to display values that round down to 0.0. A common convention is to display as '<0.1', or as appropriate with additional decimal places. Unless otherwise noted, for all percentages, the number of patients in the analysis set for the treatment group who have an observation will be the denominator. Percentages after zero counts should not be displayed and percentages equating to 100% are presented as 100%, without decimal places.
- Tabular display of data for medical history, prior/concomitant medications, and all tabular displays of adverse event data are presented by the body system, treatment class, or SOC with the highest occurrence in the active treatment group in decreasing order, assuming all terms are coded. Within

This document is confidential.

the body system, drug class and SOC, medical history (by preferred term), drugs (by ATC1 code), and adverse events (by preferred term) are displayed in decreasing order. If incidence for more than 1 term is identical, they should then be sorted alphabetically. Missing descriptive statistics or p-values which cannot be estimated are reported as “-”.

- The percentage of patients is normally calculated as a proportion of the number of patients assessed in the relevant treatment group (or overall) for the analysis set presented. However, careful consideration is required in many instances due to the complicated nature of selecting the denominator, usually the appropriate number of patients exposed. Describe details of this in footnotes or programming notes.
- For categorical summaries (number and percentage of patients) where a patient can be included in more than one category, describe in a footnote or programming note if the patient are included in the summary statistics for all relevant categories or just 1 category and the criteria for selecting the criteria.
- Where a category with a subheading (such as system organ class) has to be split over more than one page, output the subheading followed by “(cont)” at the top of each subsequent page. The overall summary statistics for the subheading should only be output on the first relevant page.

